5.2.2 Justification for the Choice of Replens® as a Predicate Device

The new VR101 and predicate Replens® devices have identical intended uses and equivalent technologies. A detailed comparison of VR101 with predicate Replens® is provided in a separate document, titled “Regulatory Comparison of the Predicate Device, Replens® Vaginal Moisturizer in Pre-Filled Applicators, with VR101”.

5.3 Study Participants

5.3.1 Inclusion Criteria for Participant Selection

Investigation Participants Must:

- Completely understand and sign the informed consent form (ability to read and understand the consent form in the English language).
- Be females 35 years of age or older.
- Express willingness to comply with the study visit schedule (see Table 4 in study procedures section).
- Over the course of the study:
 - Express willingness to abstain from the use of any vaginal moisturizers or lubricants or any other topically applied vaginal products not provided by study staff during VR101 or sham use, or during the Washout Period
 - Express willingness to abstain from the use of any HRT (hormone replacement therapy) or hormone-containing birth control products
 - Express willingness to abstain from use of any vaginal ring, diaphragm, cervical cap, or pessary products
- In the previous 60 days, have self-reported vaginal dryness that interferes with daily activities, which may include sexual intercourse

J3 Bioscience, Inc.	Clinical Investigation Plan and Protocol CI02	CI02-CIP Rev. 08 Page 29 of 75
	A Pivotal Clinical Investigation to Evaluate the Safety and Efficacy of J3 Bioscience Lubricating Intravaginal Ring VR101 in Relieving Symptoms of Vaginal Dryness	

- Present with a VHI score of 22 or less, as scored by a trained clinician during the initial visit

NOTE: At least one-third of study participants must be menopausal (must self-report that they have not experienced a menstrual period in the last 12 months). If necessary to ensure this proportion is achieved, an inclusion criterion requiring that a participant self-report to being menopausal may be added as the study progresses.

5.3.2 Exclusion criteria for participant selection

Participants self-reporting any of the following will be ineligible for study entry:

- Current use of HRT (Hormone Replacement Therapy) or any hormone-containing birth control products.
- Vulvar or vaginal procedures (biopsies, radiation) in the last 3 months.
- Active vulvar or vaginal infections/lesions or complaints, as well as undiagnosed abnormal genital bleeding.
- History of chronic pelvic pain, interstitial cystitis, vulvar vestibulitis, pelvic inflammatory disease within the past 3 months.
- Known current, clinically evident cervical or vaginal infection.
- Participants who have given birth or terminated pregnancy in the past 6 weeks.
- Postpartum or post-abortion endometritis, unless symptoms resolved at least 3 months prior to study entry.
- Current persistent, abnormal vaginal bleeding.
- History of inability to place a vaginal ring.
- History of any abnormality of the vagina resulting in distortion of the vaginal canal or incompatibility with intravaginal ring placement.
- Body habitus or history of lower genital tract abnormalities or prior surgeries which may not allow the vagina to be appropriately accessed.
- Known or suspected allergy or hypersensitivity to polyurethanes or glycerol.
- Known current alcohol or illicit drug abuse.
- Participants who have not recovered from adverse events due to chemotherapy or radiation treatment for cancer.
- Uncontrolled intercurrent illness including, but not limited to, ongoing or active infection of the urogenital tract, symptomatic congestive heart failure, unstable angina pectoris, cardiac arrhythmia, or psychiatric illness/social situations that would limit compliance with study requirements.
- Any condition that in the opinion of the investigator or study staff that would constitute contraindications to participation in the study or would compromise ability to comply with the study protocol.

J3 Bioscience, Inc.	Clinical Investigation Plan and Protocol CI02	CI02-CIP Rev. 08 Page 30 of 75
	A Pivotal Clinical Investigation to Evaluate the Safety and Efficacy of J3 Bioscience Lubricating Intravaginal Ring VR101 in Relieving Symptoms of Vaginal Dryness	

- Current use of a vaginal ring, pessary, cervical cap or diaphragm unless willingness to discontinue for the study duration is expressed.
- Pregnancy or plans to become pregnant in the next 6 months.
- Current breastfeeding and inability or unwillingness to discontinue breastfeeding for the duration of the study.

NOTE: IUD (Intrauterine Device, e.g., ParaGard®) users may be enrolled provided they commit to exercising caution when removing VR101 as IUD strings have been noted to interfere with VR101 removal.

NOTE: Participants who have previously undergone anterior and/or posterior vaginal repair and have received a vaginal mesh implant may have difficulty placing VR101, although no safety issues with VR101 use in CI01 participants who had vaginal mesh implants were noted.

5.3.3 Point of Enrollment

Participants will be considered to be enrolled upon signing the Informed Consent Form and meeting all inclusion and exclusion criteria, including inclusion criterion requiring a VHI baseline score of 22 or less. See section 8.2 for further detail regarding the VHI baseline inclusion criterion. Randomization will occur during Visit #1, following a successful VHI assessment and prior to distribution of any study articles (i.e., VR101 or sham control devices).

5.3.4 Duration of Participation

Participants will be enrolled in the study for up to 25 weeks. This will consist of a crossover study, (4 weeks of VR101/sham use, 3-week washout period, 4 weeks of sham/VR101 use), then up to 13 additional weeks VR101 use in the open-label, long-term safety evaluation, followed by a follow-up questionnaire completed 1 week after the last VR101 device is removed.

Participants will be randomly assigned to either Group S1V2 or Group V1S2. Participants in Group S1V2 will complete the crossover study (11 weeks: 4 weeks sham followed by 3 weeks wash-out followed by 4 weeks VR101) and will continue to the long-term safety evaluation (10 additional weeks, including the final follow-up call). Participants in Group V1S2 will complete the crossover study (11 weeks: 4 weeks VR101 followed by 3 weeks wash-out followed by 4 weeks sham), and will participate in the long-term safety study (13 additional weeks of VR101 use plus a final follow-up call conducted 1 week after removal of the last VR101 device [14 weeks total]).

5.3.5 Participant Withdrawal/Discontinuation

Participants may voluntarily withdraw from the investigation for any reason at any time.

J3 Bioscience, Inc.	Clinical Investigation Plan and Protocol CI02	CI02-CIP Rev. 08 Page 31 of 75
	A Pivotal Clinical Investigation to Evaluate the Safety and Efficacy of J3 Bioscience Lubricating Intravaginal Ring VR101 in Relieving Symptoms of Vaginal Dryness	

The plan for handling of incomplete efficacy study data sets (first 4 weeks of VR101 device or sham use) is described in sections 8.8 and 8.9.

If a participant discontinues VR101 use during the long-term safety evaluation, she may resume use of a fresh VR101 device at any time, provided enrollment has not been terminated. If the ring used prior to discontinuation was used for less than 5 days, then the week will need to be restarted. For example, if a participant in the safety study discontinues use of her 6th device on the 3rd day after its insertion, she will need to restart Week 6 with a fresh device, which will be inserted for the full 7 ± 2 days.

During the crossover study period, if a participant discontinues mid-week and restarts the study, the next ring must be inserted and the week will need to be restarted (similarly to the example given above), unless the ring was used for at least 5 days before the participant discontinued use. This criterion will also be applied to participants who begin a menstrual period during use, who will be instructed to remove the currently inserted ring and insert a new ring following cessation of menstruation. However, if a participant begins a menstrual period at any time during use of her 4th VR101 or sham control, she will be instructed to remove the ring, and restart with a 5th ring following cessation of menstruation. In this specific case, the participant's "28-day" efficacy evaluation actually would occur after using 5 devices instead of 4 (since it is not possible to obtain an unadulterated VHI assessment during menstruation).

Participants who report for a Study Visit during menstruation will be instructed to remove their current ring, and will re-start the study schedule per the above criteria.

NOTE: Participants who discontinue ring use mid-week and restart for any reason (including a menstrual period) will naturally deviate from the visit scheduling windows (e.g. 28±2 days) listed in Section 5.4.3. These events should be accurately recorded and documented, but do not need to be treated as formal Deviations from the Plan per Section 11. In Daily Diaries, participants will be asked to document the date and time of any such ring removal/discontinuation of use and the date and time the new ring was inserted.

All safety data will be used to test the primary safety hypothesis, except that partial ring uses will not be counted in the total number of rings used (see Endpoint 5). All participants will be automatically selected to participate in the safety portion of the investigation.

Participants who become pregnant during the study will be instructed to discontinue use of VR101 and will be dropped from the study. Study staff will refer any such participants to a clinical facility for follow-up. Efficacy datasets from these participants will be handled as described for incomplete efficacy study datasets in section 8.8 and 8.9.

J3 Bioscience, Inc.	Clinical Investigation Plan and Protocol CI02	CI02-CIP Rev. 08 Page 32 of 75
	A Pivotal Clinical Investigation to Evaluate the Safety and Efficacy of J3 Bioscience Lubricating Intravaginal Ring VR101 in Relieving Symptoms of Vaginal Dryness	

When the last participant completes the crossover study and the blind is broken, participants in Group V1S2 will be contacted by study staff and asked to discontinue VR101 use and return any remaining study products (shams or VR101 devices) to the clinic at their earliest convenience.

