Participants in Group S1V2 will be assigned to complete the long-term safety evaluation. Following the 4-week use of shams and a 3-week washout period, these participants will use a new VR101 device every 7 days for 13 consecutive weeks. V1S2 participants will be transitioned back to VR101 following 4 weeks of sham use, and will use VR101 for 13 additional weeks.

NOTE: VHI scores will be collected during the long-term safety evaluation, but those scores assigned after day 28 will not be used as a measure of device efficacy.

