5.3.8 Total Study Duration

The clinical investigation will continue until at least 60 participants have successfully enrolled in and completed the efficacy portion of the study and at least 30 participants have successfully enrolled and completed the long-term safety evaluation. This is expected to occur between 8 and 11 months (35 and 48 weeks) from initiation of the investigation, assuming the last patient enrolled is randomly assigned to complete the safety study.

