5. Participants will be instructed to remove the ring per the instructions for use and without clinician input, and will be asked to complete a post-removal survey.
6. Participants will be asked provide a urine sample for a pregnancy test.
7. Participants will be asked to complete an End-of-Use survey.

J3 Bioscience, Inc.	Clinical Investigation Plan and Protocol CI02	CI02-CIP Rev. 08 Page 40 of 75
	A Pivotal Clinical Investigation to Evaluate the Safety and Efficacy of J3 Bioscience Lubricating Intravaginal Ring VR101 in Relieving Symptoms of Vaginal Dryness	

8. During Visit 6, the Participant will be given a package containing the Participant Number followed by the letter “C” (for example Participant 1 will be given a package labeled “1C”) regardless of her randomization status. This package will contain 12 each VR101 devices (one for each week and 3 spares) and will be instructed to insert a new ring, again per the instructions for use and without clinician input.
9. Participants will be asked to complete a Post-Insertion survey.
10. During Visits 3 and 6, participants will be asked to return any additional unused devices (spares) left over from the previous package.
11. Devices administered will be used consecutively, each to remain in the vagina for 7 ± 2 days.

Final Visit (can be used for Participants who withdraw from the study between scheduled Visits)

1. When the crossover study blind is broken, V1S2 participants still using VR101 will be contacted and asked to discontinue VR101 use. A visit will be scheduled for the participant to return study products and disclose any Adverse Events or concomitant medication changes.
2. During the Visit, participants will be asked to provide a urine sample for a pregnancy test.

Visit 7 (all)/Visit 8 (V1S2 only) - Long-Term Safety Visit

1. Participants still enrolled in the study will return to the clinic on day 105/140 (± 2 days).
2. Participants will be asked to report any Adverse Events (AEs), whether or not they feel they were related to use of the investigational device. AEs will be recorded on the Adverse Event Form (Attached).
3. Participants will be asked to complete a Pre-Procedure Survey.
4. Participants will undergo a brief vaginal health assessment that will include a pH test and assessment of Vaginal Health Index (VHI) (see Table 6).

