5. Participants will be instructed to remove the ring per the instructions for use and without clinician input, and will be asked to complete a post-removal survey.
6. Participants will be asked to provide a urine sample for a pregnancy test.
7. Participants will be asked to insert a new ring per the instructions for use and without clinician input, and to complete a post-insertion survey.
8. This device and 3 additional VR101 devices will be used consecutively, each to remain in the vagina for 7 ± 2 days.
9. During Visit 8, V1S2 participants will be given 4 additional VR101 devices

J3 Bioscience, Inc.	Clinical Investigation Plan and Protocol CI02	CI02-CIP Rev. 08 Page 41 of 75
	A Pivotal Clinical Investigation to Evaluate the Safety and Efficacy of J3 Bioscience Lubricating Intravaginal Ring VR101 in Relieving Symptoms of Vaginal Dryness	

Visit 8 (S1V2) or Visit 9 (V1S2) - Final Long-Term Safety Visit

1. Participants will return to the clinic on day 140 (S1V2) or day 168 (V1S2) (\pm 2 days).
2. Participants will be asked to report any Adverse Events (AEs), whether or not they feel they were related to use of the investigational device. AEs will be recorded on the Adverse Event Form (Attached).
3. Participants will be asked to complete a Pre-Procedure Survey.
4. Participants will undergo a brief vaginal health assessment that will include a pH test and assessment of Vaginal Health Index (VHI) (see Table 6).
5. Participants will be instructed to remove the ring per the instructions for use and without clinician input, and will be asked to complete a post-removal survey.
6. Participants will be asked to provide a urine sample for a pregnancy test.
7. Participants will be asked to complete an End-of-Use survey.
8. Participants will be asked to return all unused rings to the clinic.

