8.4 Expected Drop-Out Rates

NOTE: The first paragraph below contains out-of-date information, as of this Revision, but is included for reference.

During the pilot investigation (CI01), one participant missed multiple study visits and discontinued the VR101 treatment regimen. However, the participant eventually restarted and successfully completed the investigation, meaning that the drop-out rate for CI01 was 0%. Statistically, if the dropout rate is “0” for a sample size of 21, we can then rule out any drop-out rates higher than 14.6% with 95% confidence (upper bound of the exact Blyth-Still-Casella confidence interval for the proportion 0/21). However, since CI02 requires longer continued participant involvement than CI01, it is possible that the drop-out rate for enrolled participants in CI02 may even exceed 14.6%. We have assumed a 14.6% dropout rate to estimate the number of participants to enroll in the proposed investigation.

The 95% confidence interval used above still underestimated the drop-out rate due to the differing enrollment durations of CI01 and CI02. During the crossover study, which lasted for 11 weeks (per participant), 11 of 72 participants withdrew from the study (1.39% of initial enrollment per week [average], 0.70-2.47% per week [95% CI]. Assuming that half of the participants will participate in the long-term safety study for 9 weeks (Group S1V2) and the remaining half will participate for 13 weeks (Group V1S2), continuation of at least 42 total participants will ensure, with 95% confidence, that 30 participants will complete the long-term safety evaluation (13 consecutive weeks of VR101 use).

Since participants will need to be re-consented when this protocol revision takes effect, the number of additional dropouts (not accounted for by the calculation above) when participants are presented with the new Informed Consent Form is unknown. Therefore, we will offer

J3 Bioscience, Inc.	Clinical Investigation Plan and Protocol CI02	CI02-CIP Rev. 08 Page 55 of 75
	A Pivotal Clinical Investigation to Evaluate the Safety and Efficacy of J3 Bioscience Lubricating Intravaginal Ring VR101 in Relieving Symptoms of Vaginal Dryness	

participation in the long-term safety study to all available participants (up to 61) to ensure that the goal, of 30 participants using VR101 continuously for 13 weeks in the safety portion of the investigation, is met.

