9 DATA COLLECTION AND MANAGEMENT

Paper CRFs (Case Report Forms) will be used for data collection during the study. Paper CRFs will be printed on 2-part NCR (no carbon required) with a copy retained by the investigators at the conclusion of the study.

Data from CRFs will be transcribed into an electronic database by the sponsor using double data-entry following study opening. Since the hand-written original CRF copies will serve as the official study record, Sponsor/analyst bias does not present concern to the study, provided double data-entry and an additional, independent data audit of database transfer is performed.

Following the final participant's Visit 6, data from the comparative efficacy (crossover) study (all data from Visits 1-5 and all data from Visit 6 except for the Post-Insertion survey) can be locked and the study blind can be broken. At this time, comparative efficacy (crossover) study data will be available for analysis.

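### Sections 5.3.5 and 5.4.3 still tell V1S2 women to stop VR101 when the crossover blind is broken, although Rev. 08 needs them to use it for 13 weeks to reach 30 long-term completers

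*Combined protocol and SAP*

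**What the plan says.** **The stop.** Section 5.3.5 states that when the last participant completes the crossover and the blind is broken, "participants in Group V1S2 will be contacted by study staff and asked to discontinue VR101 use" and return their remaining rings. Item 1 of the Final Visit text in Section 5.4.3 repeats it: on unblinding, "V1S2 participants still using VR101 will be contacted and asked to discontinue VR101 use". Section 9 says that after the final participant's Visit 6 the crossover data "can be locked and the study blind can be broken".

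**The 13 weeks.** Section 5.1 says "V1S2 participants will be transitioned back to VR101 following 4 weeks of sham use, and will use VR101 for 13 additional weeks". Sections 1.4 and 5.3.4 agree. Table 4 and the final long-term safety visit in 5.4.3 bring V1S2 women back at day 168.

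**The numbers.** Section 8.4 takes half of those continuing as S1V2 for 9 weeks and says "the remaining half will participate for 13 weeks (Group V1S2), continuation of at least 42 total participants will ensure, with 95% confidence", that 30 will complete. It adds that up to 61 women will be offered continuation. Section 5.3.8 keeps the investigation open until "at least 30 participants have successfully enrolled and completed the long-term safety evaluation".

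**The concern.** The two sets of instructions cannot both be followed for a V1S2 woman who is still within her 13 weeks when the blind is broken. Visit 6 is at day 77 and her last visit at day 168, so she needs 91 days (13 weeks) after Visit 6. If the blind is broken at the earliest permitted time and visits run on schedule, every V1S2 woman enrolled less than 13 weeks before the last participant is stopped before she completes.

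The Synopsis gives the purpose of Rev. 08 as securing enough participants to complete the long-term safety evaluation, and it does so by bringing V1S2 women into that evaluation. The stop removes the same women. Section 5.3.6 allows replacement enrolment only while the blind is unbroken, so new enrolment could not repair a shortfall caused by the stop. What is at stake is the stated minimum of 30 women with 13 consecutive weeks of use.

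**Working it through.** **1. Reproduce Section 8.4.** Inputs from 8.4: 11 of 72 withdrew over 11 weeks; 9 further weeks for S1V2 and 13 for V1S2; equal halves.

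- Weekly rate r = 11/(72 × 11) = 11/792 = 1.39%. The exact 95% interval is 0.70% to 2.47%, as printed.
- With m continuing and linear loss, completers = (m/2)(1 − 9r) + (m/2)(1 − 13r).
- At r = 2.47%, m = 41 gives 29.9 and m = 42 gives 21 × 0.7777 + 21 × 0.6789 = 16.3 + 14.3 = 30.6. The smallest m that reaches 30 is therefore 42, the plan's figure.

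About 14 of the 30.6 completers are V1S2 women.

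**2. Worst case: no V1S2 woman has finished when the stop applies.** Only the S1V2 term, (m/2)(1 − 9r), remains. The split of the 61 is not stated; equal halves are assumed.

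| Continuing | r = 2.47% | r = 1.39% |
|---|---|---|
| 42 | 21 × 0.7777 = 16.3 | 21 × 0.8749 = 18.4 |
| 61 | 30.5 × 0.7777 = 23.7 | 30.5 × 0.8749 = 26.7 |

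At the lower limit of 0.70%, 61 continuing gives 30.5 × 0.937 = 28.6, still below 30.

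**3. Allow for V1S2 women who finish before the stop.** Accrual dates are not in the documents. Section 5.3.7 estimates 10 to 23 weeks; 72 women at its slower rate of 3 per week would take 24. Assume uniform accrual over T weeks, equal groups, on-schedule visits and unblinding at the last Visit 6. The fraction of V1S2 women already past week 13 is f = max(0, (T − 13)/T), and completers = (m/2)[(1 − 9r) + f(1 − 13r)].

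| T (weeks) | f | 42 continuing: 2.47% / 1.39% | 61 continuing: 2.47% / 1.39% |
|---|---|---|---|
| 10–13 | 0 | 16.3 / 18.4 | 23.7 / 26.7 |
| 16 | 0.19 | 19.0 / 21.6 | 27.6 / 31.4 |
| 24 | 0.46 | 22.9 / 26.3 | 33.2 / 38.1 |

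With 42 continuing, the expected number stays below 30 at every accrual length considered.

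**4. Break-even with 61 continuing.** Solve for 30 completers, then T = 13/(1 − f).

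- r = 1.39%: f = (30 − 26.68)/24.99 = 0.133, so T = 15.0 weeks.
- r = 2.47%: f = (30 − 23.72)/20.71 = 0.303, so T = 18.7 weeks.
- r = 0.70%: f = (30 − 28.58)/27.72 = 0.051, so T = 13.7 weeks.

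**5. Does anything in the text cancel the stop?** The carry-over note in 5.4.3 covers the EOT visit and the final phone call of Table 4. The out-of-date note in 8.4 covers one paragraph on drop-out. Neither mentions the stop.

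**6. Does the stop reach the safety denominator?** Section 8.3 counts 30 × 13 + 30 × 4 = 510 devices. The second group of 30 is credited with four crossover rings each, so no V1S2 long-term rings are included.

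**The case against.** The case for treating this as a minor wording matter has four parts.

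- **The Final Visit text may already be flagged.** Its heading says it can be used for women who withdraw between visits, which closely matches the EOT footnote to Table 4, and 5.4.3 says the EOT visit is carried over and not needed for completers. The resemblance is real. But item 1 is triggered by unblinding, not withdrawal, and is addressed to women still using VR101. The sentence in 5.3.5 has no such limit.
- **The sponsor controls the trigger.** Section 9 permits unblinding but sets no date, and 5.3.8 could support waiting. This stands as a way to avoid the harm. However, nothing ties unblinding to V1S2 completion, and 8.6 makes the crossover data available for analysis after the last Visit 6.
- **The intent is clear.** Most of Rev. 08, including the extra rings dispensed to V1S2 women at Visit 8, shows they are meant to continue. A careful site would probably ask before stopping anyone. That lowers the chance of harm but leaves sites with two opposite written instructions.
- **The figures for 42 are a floor.** Section 8.4 offers continuation to as many as 61, and with slow accrual 61 is enough. This stands, and it limits the size of the point. Loss at re-consent, which 8.4 calls unknown, would work the other way.

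**Conclusion.** The inconsistency is real and is in current text. Followed literally at the earliest permitted unblinding, the stop can leave fewer than 30 women with 13 consecutive weeks of use. The expected number is 16 to 26 if 42 continue. If all 61 continue, it is 24 to 38, depending on accrual length and drop-out, and reaches 30 only with accrual of at least about 15.0 weeks (1.39%) or 18.7 weeks (2.47%). These ranges rest on uniform accrual over 10 to 24 weeks, equal groups, linear loss at the two rates and unblinding at the last Visit 6.

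The consequence is limited to the long-term exposure target. The crossover efficacy analysis and the 510-device basis of 8.3 do not change, and 30 completers is not a pass/fail criterion under 8.5. It should be fixed because the leftover instruction works against the amendment's own purpose.

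**What to change.** Delete the discontinuation sentence in 5.3.5 and item 1 of the Final Visit text in 5.4.3, or limit both to V1S2 women who decline re-consent or withdraw from the long-term phase. Suggested wording: *When the crossover blind is broken, V1S2 participants continue VR101 through Visit 9 (day 168); those who declined or withdrew will be asked to return remaining study products.*

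Unblinding gives no reason to stop: 5.3.4 calls the long-term evaluation open-label, and at Visit 6 every woman receives VR101 whatever her randomization. With this change 8.4 stands as written and 8.3 needs no recalculation.

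The cost is two edits, the sponsor and IRB approval that Section 10 requires, and a notice to sites. It adds no participants, visits or devices to the amended design.
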